1 PROTOCOL SUMMARY

1.1 SYNOPSIS

| | |
|---------------------------|--|
| Title: | Care partner assisted intervention to improve oral health of individuals with mild dementia |
| Grant Number: | U01DE027512 |
| Study Description: | Open label, randomized, multisite trial to study oral health intervention in individuals with mild dementia and their care partners at two sites. The recruited dyads, each consisting of an individual with mild dementia (participants) and his/her care partner will be randomly assigned to one of three groups, treatment group 1, treatment group 2, and control group. The first three months will be the active treatment phase and the final three months will be the maintenance phase. Data from each dyad will be collected over a period of six months. Oral health outcomes will be compared between the control and treatment groups. |
| Objectives: | |
| Objective 1: | To evaluate the efficacy of an intervention to improve oral hygiene clinical outcomes (i.e. plaque index and gingival index) by improving oral hygiene behavior (i.e., frequency and duration of toothbrushing) and oral health skills among individuals with mild dementia. |
| Objective 2A: | To determine whether effects of the intervention [X] on oral hygiene behavioral outcomes [Y] , are mediated by the following variables from the care partners' perspective: 1) oral care self-efficacy; 2) care partner self-efficacy; 3) use of cueing methods; 4) and FOCUSED Communication. |
| Objective 2B: | To determine whether effects of the intervention [X] on oral hygiene clinical outcomes [Y] , are mediated by the following variables from the care partner's perspective: 1) oral care self-efficacy; 2) care partner's self-efficacy; 3) use of cueing methods; 4) and FOCUSED Communication. |
| Objective 3a: | To determine whether effects of the intervention [X] on oral hygiene clinical outcomes [Y] are mediated by oral hygiene behavioral outcomes [M] . |
| Objective 3b: | To determine whether effects of the intervention [X] on oral hygiene clinical outcomes [Y] is mediated by the care partner's |

factors [M1], which then mediates the oral hygiene behavioral outcomes [M2] on oral hygiene clinical outcomes [Y].

Endpoints:

Primary Endpoint:

Oral Hygiene Clinical Outcomes

1. Plaque Index
2. Gingival Index

Secondary Endpoints:

Oral Hygiene Behaviors

1. Frequency of brushing
2. Duration of brushing

Oral hygiene skill

- Hygienist assessment of thoroughness and technique of participant's usual brushing and flossing

Study Population:

120 Individuals with mild dementia and their care partners. This number may be increased up to 150 if attrition rates are higher than the initial prediction.

Phase or Stage:

Phase II

Description of Sites/Facilities

At NYU, we will recruit participants from:

Enrolling Participants:

1) NYU Alzheimer's Disease Center (ADRC), a part of the Department of Neurology at NYU School of Medicine. The ADRC currently has an active cohort of 363 participants, of which 20% are mildly cognitively impaired, and 9% have Alzheimer's disease or related dementia.
2) Pearl I. Barlow Center for Memory Evaluation and Treatment at NYU Langone School of Medicine. Approximately 420 patients with mild dementia visit the Center annually.

At Duke, we will recruit from:

1) Duke Memory Disorders Clinic (Duke MDC). The Duke MDC sees an estimated 600 new patients and about 1700 return patients each year; about 40% of these are in the mild dementia range.

At both sites, we will also recruit via alliances with clinical specialists at other medical facilities and at various venues including medical centers, dementia support groups, and community facilities, organizations and events.

Description of Study Intervention:

[figure not shown]
Our design includes three groups:

[figure not shown]
- Control Group will receive an educational booklet only and will continue their usual brushing techniques (manual or electric).
- Treatment Group 1 will receive educational booklet and a smart electronic toothbrush.
- Treatment Group 2 will receive the booklet, a smart electronic toothbrush, and in-home and telephone coaching.

Study Duration: 36 months

[figure not shown]
Participant Duration: 6 months

1.2 SCHEMA

[figure not shown]

* Includes an Oral Health Evaluation (plaque index, gingival index, denture plaque index, OHAT); Assessment of oral hygiene behaviors (oral hygiene skill, frequency and duration of brushing); administration of questionnaires for participant and care partner (demographics, medical and dental history, dental care utilization, dental care needs, oral hygiene care, oral health knowledge, self-efficacy in brushing behavior, Adaptive Leadership Self-Efficacy, Adaptive Leadership Behaviors – Cueing, and Adaptive Leadership Behaviors – FOCUSED Communication.

* Includes an Oral Health Evaluation (plaque index, gingival index, denture plaque index, OHAT); Assessment of oral hygiene behaviors (oral hygiene skill, frequency and duration of brushing); administration of questionnaires for participant and care partner including demographics, medical and dental history, dental care utilization, dental care needs, oral hygiene care, oral health knowledge, self-efficacy in brushing behavior, Adaptive Leadership Self-Efficacy, Adaptive Leadership Behaviors – Cueing, and Adaptive Leadership Behaviors – FOCUSED Communication.

1.3 SCHEDULE OF ACTIVITIES

Treatment Group 1

| Treatment Group 1 | Screening | Time 1 (Home Visit 1) Week 1: (within 42 days of screening) | Time 2 Week 4: (± 7 Days) | Time 3 Week 8: (± 7 Days) | Time 4 (Home Visit 2) Week 12: (± 14 Days) | Time 5 Week 16: (± 7 Days) | Time 6 Week 20: (± 7 Days) | Time 7 (Home Visit 3) Week 24: (± 14 Days) |
|-------------------------------------|-----------|--|---------------------------------|---------------------------------|---|----------------------------------|----------------------------------|---|
| Screen for eligibility | X | | | | | | | |
| Obtain verbal informed consent | X | | | | | | | |
| Schedule Visit 1 | X | | | | | | | |
| Obtain written informed consent | | X | | | | | | |
| Care Partner Questionnaire | | X | | | X | | | X |
| Study Participant Questionnaire | | X | | | X | | | X |
| Oral Health Evaluation | | X | | | X | | | X |
| ADCS-ADL | | X | | | | | | |
| Oral Hygiene Skill Assessment Sheet | | X | | | X | | | X |
| Coaching Module | | | | | | | | |
| Tailored Oral Hygiene Instruction | | | | | | | | |

| Treatment Group 1 | Screening | Time 1 (Home Visit 1) Week 1: (within 42 days of screening) | Time 2 Week 4: (± 7 Days) | Time 3 Week 8: (± 7 Days) | Time 4 (Home Visit 2) Week 12: (± 14 Days) | Time 5 Week 16: (± 7 Days) | Time 6 Week 20: (± 7 Days) | Time 7 (Home Visit 3) Week 24: (± 14 Days) |
|---|-----------|--|---------------------------------|---------------------------------|---|----------------------------------|----------------------------------|---|
| Montreal Cognitive Assessment (MoCA) | | X | | | X | | | X |
| Educational booklet provided | | X | | | | | | |
| Electronic Toothbrush Data Download | | | X | X | X | X | X | X |
| Detailed explanation of education booklet | | | | | | | | X |
| Exit Interview w/participant | | | | | | | | X |
| Exit Interview w/care partner | | | | | | | | X (via phone) |

Treatment Group 2

| Treatment Group 2 | Screening | Time 1 (Home Visit 1) Week 1: (within 42 days) | Time 2 Week 4: (± 7 Days) | Time 3 Week 8: (± 7 Days) | Time 4 (Home Visit 2) Week 12: (± 14 Days) | Time 5 Week 16: (± 7 Days) | Time 6 Week 20: (± 7 Days) | Time 7 (Home Visit 3) Week 24: (± 14 Days) |
|---------------------------------|-----------|---|---------------------------------|---------------------------------|---|----------------------------------|----------------------------------|---|
| Screen for eligibility | X | | | | | | | |
| Obtain verbal informed consent | X | | | | | | | |
| Schedule Visit 1 | X | | | | | | | |
| Obtain written informed consent | | X | | | | | | |
| Care Partner Questionnaire | | X | | | X | | | X |
| Study Participant Questionnaire | | X | | | X | | | X |
| Oral Health Evaluation | | X | | | | | | |
| ADCS-ADL | | X | | | | | | |

| Treatment Group 2 | Screening | Time 1 (Home Visit 1) Week 1: (within 42 days) | Time 2 Week 4: (± 7 Days) | Time 3 Week 8: (± 7 Days) | Time 4 (Home Visit 2) Week 12: (± 14 Days) | Time 5 Week 16: (± 7 Days) | Time 6 Week 20: (± 7 Days) | Time 7 (Home Visit 3) Week 24: (± 14 Days) |
|---|-----------|---|---------------------------------|---------------------------------|---|----------------------------------|----------------------------------|---|
| Oral Hygiene Skill Assessment Sheet | | X | | | X | | | X |
| Coaching Module | | X | X (via phone) | X (via phone) | X | | | |
| Tailored Oral Hygiene Instruction | | X | | | X | | | |
| Montreal Cognitive Assessment (MoCA) | | X | | | X | | | X |
| Educational booklet provided and reviewed | | X | | | | | | |
| Electronic Toothbrush Data Download | | | X | X | X | X | X | X |

| Treatment Group 2 | Screening | Time 1 (Home Visit 1) Week 1: (within 42 days) | Time 2 Week 4: (± 7 Days) | Time 3 Week 8: (± 7 Days) | Time 4 (Home Visit 2) Week 12: (± 14 Days) | Time 5 Week 16: (± 7 Days) | Time 6 Week 20: (± 7 Days) | Time 7 (Home Visit 3) Week 24: (± 14 Days) |
|--|-----------|--|---------------------------------|---------------------------------|--|----------------------------------|----------------------------------|--|
| Post Intervention Interview—participant | | | | | X | | | |
| Post Intervention Interview-Care partner | | | | | X (via phone) | | | |
| Exit Interview w/participant | | | | | | | | X |
| Exit Interview w/care partner | | | | | | | | X (via phone) |

Control Group

| Control Group | Screening | Time 1 (Home Visit 1) Week 1: (within 42 days) | Time 2 Week 4: (± 7 Days) | Time 3 Week 8: (± 7 Days) | Time 4 (Home Visit 2) Week 12: (± 14 Days) | Time 5 Week 16: (± 7 Days) | Time 6 Week 20: (± 7 Days) | Time 7 (Home Visit 3) Week 24: (± 14 Days) |
|-------------------------------------|-----------|---|---------------------------------|---------------------------------|---|----------------------------------|----------------------------------|---|
| Screen for eligibility | X | | | | | | | |
| Obtain verbal informed consent | X | | | | | | | |
| Schedule Visit 1 | X | | | | | | | |
| Obtain written informed consent | | X | | | | | | |
| Care Partner Questionnaire | | X | | | X | | | X |
| Study Participant Questionnaire | | X | | | X | | | X |
| Oral Health Evaluation | | X | | | X | | | X |
| ADCS-ADL | | X | | | | | | |
| Oral Hygiene Skill Assessment Sheet | | X | | | X | | | X |
| Coaching Module | | | | | | | | |
| Tailored Oral Hygiene Instruction | | | | | | | | |

| Control Group | Screening | Time 1 (Home Visit 1) Week 1: (within 42 days) | Time 2 Week 4: (± 7 Days) | Time 3 Week 8: (± 7 Days) | Time 4 (Home Visit 2) Week 12: (± 14 Days) | Time 5 Week 16: (± 7 Days) | Time 6 Week 20: (± 7 Days) | Time 7 (Home Visit 3) Week 24: (± 14 Days) |
|---|-----------|---|---------------------------------|---------------------------------|---|----------------------------------|----------------------------------|---|
| Montreal Cognitive Assessment (MoCA) | | X | | | X | | | X |
| Educational booklet provided | | X | | | | | | |
| Detailed explanation of education booklet | | | | | | | | X |
| Electronic Toothbrush Data Download | | | | | | | | |
| Post Intervention Interview— participant | | | | | | | | |
| Post Intervention Interview—Care partner | | | | | | | | |
| Distribution of a smart electronic toothbrush | | | | | | | | X |
| Exit Interview w/participant | | | | | | | | X |
| Exit Interview w/care partner | | | | | | | | X (via phone) |

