6 STUDY INTERVENTION(S) OR EXPERIMENTAL MANIPULATION(S)

6.1 STUDY INTERVENTION(S) OR EXPERIMENTAL MANIPULATION(S) ADMINISTRATION

6.1.1 STUDY INTERVENTION OR EXPERIMENTAL MANIPULATION DESCRIPTION

Control Group

The Control group intervention includes a standard educational booklet and clinical oral health evaluation with no instruction on oral hygiene technique. The educational booklet is the same one delivered to the intervention groups. The oral health evaluation is detailed in procedures below. The dental hygienist will observe the participant's normal toothbrushing technique, interdental cleaning procedures, and the cleaning of partial dentures. No instruction is provided.

Treatment Group 1

The Treatment group 1 intervention includes the standard educational booklet, clinical oral health evaluation and a smart electronic toothbrush with no instruction on oral hygiene technique. The educational booklet is the same standard one that is delivered to all groups. The oral health evaluation is detailed in procedures below. The dental hygienist will observe the participant's normal toothbrushing technique, interdental cleaning procedures, and the cleaning of partial dentures. No instruction is provided. The hygienist will provide basic instruction on proper use of the smart electronic toothbrush.

Treatment Group 2

The Care Partner-Assisted Intervention includes the standard educational booklet, clinical oral health evaluation with tailored instruction on oral hygiene technique, and care partner coaching. These components are summarized in Table 2 (below). The two intervention components (i.e., tailored instruction and coaching) are interrelated and thus the hygienist and interventionist work together as described below.

Table 2: Care Partner (CP) Assisted Intervention Components

| Component | Who/Where | When |
|--|--|--|
| 1. In-home oral exam | Participant, CP, hygienist, and interventionist | · Baseline · 3 months. · 6 months. |
| 
 Oral health educational booklet, given on first visit Oral health evaluation Assessment of technical challenges and tailored instruction on oral hygiene technique Create Oral Hygiene Treatment Plan using Dental Hygienist's Guidance), given on baseline visit and 3-month visit List tailored recommendations for oral care for dyad (to be integrated in care partner assisted coaching modules), given on baseline visit and 3-month visit Monitoring of oral hygiene by dyad | Home visit | |

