*Target accrual: 120 dyads

Study Design

This is a three parallel arm randomized controlled trial (RCT) to evaluate the effectiveness of a care partner-assisted intervention to improve oral hygiene in individuals (≥ 60 years) with mild dementia. Participant-care-partner dyads were randomized into 1 of 3 groups: Treatment Group 1 (**TG1**), Treatment Group 2 (**TG2**), and the Control Group (**CG**) stratified by site. **TG1** and **TG2** were given smart electronic toothbrushes. Only **TG2** will receive in-home and telephone coaching throughout the duration of the study and were instructed to record daily brushing habits. The coaching sessions included individualized instruction on oral hygiene technique, cueing strategy development, or oral hygiene monitoring and coaching. **TG1** and **CG** did not receive coaching sessions. While randomization occurred at the dyad level (participant-care partner), primary study outcomes will be assessed at the participant level. The study duration was 6 months, including a 3 month intervention phase, in which coaching and educational modules were delivered, followed by a 3 month maintenance phase in which no coaching or educational modules were presented to participants. Data was collected by the study team at three visits: baseline, 3-months (end of active intervention phase), and 6-months (end of three-month maintenance phase). The primary endpoint is oral hygiene (plaque index, gingival index) at 3 months, with a secondary endpoint of 6 months to explore maintenance of intervention effects.

Study Aims

Aim 1: Evaluate the effectiveness of a care partner-assisted intervention to improve oral hygiene and oral hygiene behaviors in individuals with mild dementia.

Hypothesis 1a: Compared to CG, both T1 and T2 will result in improved oral hygiene as measured by reduced plaque index, and reduced gingival index, at 3 months.

Hypothesis 1b: T2 will have higher improvement than T1, relative to CG, in oral hygiene as measured by a greater reduction in plaque index, and gingival index, at 3 months.

Aim 2: Assess changes in mediating factors/process outcomes, including communication between the dyads, oral health knowledge, and self-efficacy for both participants and care partners to understand mechanisms of the intervention.

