General Approach: The overall goal of this study is to demonstrate the effectiveness of the two intervention strategies (TG1, TG2) against that of CG. The primary outcomes are plaque index, which is quantified as the proportion of sites with plaque deposits on at least less than 1/3 of crown, and gingival index, which is quantified as the proportion of sites with at least some mild inflammation. While the unit of randomization is at the dyad level, the primary outcomes will be evaluated at the individual level. As participants and care-partners contribute repeated measures (at baseline, 3 months and 6 months), we will use a linear mixed modeling approach for the analysis of the primary hypotheses, to account for correlation among repeated measures from the same individual. Analyses for all study outcomes will be conducted according to the intention-to-treat (ITT) principle, where all participants are analyzed according to the group in which they were randomized, irrespective of their receipt of allocated treatment. For our primary analysis we will conduct a

complete case analysis, thus excluding participants who are lost to follow up. As a sensitivity analysis, we will use the strategy of last-observation-carried-forward (LOCF) (thus assuming no change), to impute missing values for participants lost to follow up, if a monotone pattern is demonstrated in complete data. A strategy of LOCF is conservative in that it may bias results towards a null effect, but eliminates bias related to differential dropout, especially in the case where participants with no improvement are less likely to complete follow-up assessments. Statistical analyses will be performed in R version 4.4.0. All statistical tests will be two-sided, and a p-value of < 0.05 will be considered statistically significant.

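### The Treatment Group 2 schedule marks the Oral Health Evaluation, which yields both primary outcomes, at baseline only, contradicting Table 2, Sections 4.1 and 8.2, and the SAP

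*Combined protocol and SAP*

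**What the plan says.** Protocol Section 1.3 gives one schedule table per arm, each with a screening column and seven timepoints. In the TG1 and Control tables the row reads "Oral Health Evaluation | | X | | | X | | | X", which places the evaluation at Time 1, Time 4 (Week 12) and Time 7 (Week 24). In the TG2 table the row begins in the same way, "Oral Health Evaluation | | X", but every cell after Time 1 is blank.

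The footnote to the schema in Section 1.2 says what is assessed: "Includes an Oral Health Evaluation (plaque index, gingival index, denture plaque index, OHAT" and other items. Both primary outcomes are therefore scored inside this evaluation.

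Table 2 in Section 6.1.1 describes the TG2 intervention specifically. It lists the in-home oral exam, with the oral health evaluation as one of its parts, at "Baseline · 3 months. · 6 months". The SAP, under Study Design, states: "The primary endpoint is oral hygiene (plaque index, gingival index) at 3 months, with a secondary endpoint of 6 months".

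**The concern.** The schedule of activities is the page that site staff work from. Section 4.4 itself refers to it when defining the end of the study. For the arm that carries the coaching intervention, that page omits the primary outcome assessment at both post-baseline visits, while other text requires or assumes it.

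Staff holding the protocol therefore have two incompatible instructions for TG2 at Weeks 12 and 24. Section 10.1.10 treats any noncompliance with the protocol as a deviation, so neither performing nor omitting the evaluation is cleanly compliant. If some visits followed the row and others followed Table 2, the primary outcome would be missing in one arm only, for a reason tied to assignment. The SAP's primary approach, a "complete case analysis, thus excluding participants who are lost to follow up", would not repair that. Its sensitivity analysis by last observation carried forward is written for participants lost to follow-up. If it were applied to attended but unscored TG2 visits, it would carry baseline forward and impose zero change on that arm.

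**Working it through.** The plan states no figure to reproduce. The check sets the passages side by side and then counts.

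**1. The three schedule rows (Section 1.3).** Each row has 8 cells after the label: screening plus Times 1 to 7.

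| Arm | Cells | Marks | Visits marked |
|---|---|---|---|
| TG1 | 8 | 3 | Weeks 1, 12, 24 |
| TG2 | 8 | 1 | Week 1 |
| Control | 8 | 3 | Weeks 1, 12, 24 |

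The TG2 row has its full number of cells, so no column has dropped out. The TG2 rows for both questionnaires, the skill assessment and the MoCA keep their Week 12 and Week 24 marks.

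**2. Text that conflicts with the TG2 row.**
- Section 6.1.1, Table 2 (TG2 only): "1. In-home oral exam | Participant, CP, hygienist, and interventionist | · Baseline · 3 months. · 6 months".
- Section 6.1.1, paragraph on the clinical oral health evaluation: labelled as applying to all groups.
- Section 4.1: the team, including the hygienist, makes three visits, and the hygienist does an oral health evaluation during the visit.
- Section 6.1.2: the three home visits are justified by the need for baseline, 3-month and 6-month measures.
- Section 8.2: refers to an oral evaluation at every study visit, with no arm excepted.
- Section 9.2: assumes outcome data at all three time points.
- SAP, Study Design and Study Aims: Hypotheses 1a and 1b compare plaque and gingival indices at 3 months, including in TG2.
- The TG2 schedule itself marks Tailored Oral Hygiene Instruction at Week 12. Section 6.1.1 says the evaluation guides the tailored recommendations and that the plan is provided at baseline and Visit 2.

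**3. Size of the gap if the row were followed literally.** Inputs: target 120 dyads (Section 9.2 and SAP), equal allocation (Section 6.3), and completers as of 05/08/24 of 18 in TG1, 17 in TG2 and 19 in Control. Post-baseline evaluations per participant are 2 where the row has three marks and 0 in the TG2 row.
- Planned size: 120 / 3 = 40 per arm. All arms: 120 × 2 = 240. TG2: 40 × 2 = 80. Share lost: 80 / 240 = 33%.
- Completers: 18 + 17 + 19 = 54. All arms: 54 × 2 = 108. TG2: 17 × 2 = 34. Share lost: 34 / 108 = 31%.

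In both cases the whole loss falls in one arm.

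**4. What could still be estimated.** The SAP model for Aim 1 has group, time and group-by-time terms for 3 groups at 3 times, hence 3 × 3 = 9 cell means and (3 − 1) × (3 − 1) = 4 interaction coefficients. On the literal reading, the TG2 cells at 3 and 6 months are empty, leaving 7 cells with data. The two TG2-by-time coefficients have no data behind them, so TG2 versus control and TG2 versus TG1 (Hypothesis 1b) are lost at both times. The two TG1-by-time coefficients, and TG1 versus control at 3 and 6 months, remain estimable.

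**The case against.** The strongest reply is that this is a clerical slip with no practical effect. The row is the only text implying a baseline-only evaluation in TG2. Everything listed in step 2 of the working points the other way, and Table 2, written for this very arm, contradicts the row directly. Trained hygienists attending all three visits would be unlikely to omit the study's main measurement. Most of this stands: the point is an internal contradiction, not a design decision, and an omission in the table is the likely explanation.

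A second reply is that two marks may have been lost when the PDF was converted to text; the row sits near a page break, and its pattern matches the ADCS-ADL row beneath it. The intact cells and the marks kept in neighbouring TG2 rows make this unlikely, but the original page should be checked.

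A third reply is that an amendment cannot change visits already held. That is correct, and it is why correcting the row is not enough by itself.

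None of these replies removes the contradiction from an operative table, or shows that every TG2 visit was scored.

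**Conclusion.** The TG2 row is wrong as written and conflicts with several other parts of the protocol and with the SAP. The 33% and 31% shares describe what a literal reading would cost; they do not estimate data actually lost. The completer count assumes that the table's completed column uses the Section 4.4 definition.

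A reader might infer that TG2 has no follow-up plaque or gingival scores, for example that 0 of its 20 consented dyads were scored at 3 or 6 months. The documents do not support that. The SAP's Study Design describes, in the past tense, data collection at three visits with no arm excepted. It follows a table listing 17 TG2 dyads as completed, and Section 4.4 makes both later visits part of completion. Section 4.4 does not mention scoring, however, so completed visits are reassuring without being proof.

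A reader might also infer that the whole group-by-time analysis would fail. That goes too far: only the TG2 terms and contrasts depend on the missing cells.

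**What to change.** 1. Reconcile the TG2 row in Section 1.3 with Table 2, Sections 4.1, 6.1.1 and 8.2, and the SAP, so that the visits at which the plaque and gingival indices are scored are stated identically for all three arms.
2. Before analysis, confirm from source records that 3-month and 6-month plaque and gingival scores exist for TG2, and report the number of participants scored by arm and visit.
3. If any TG2 visit was held without scoring because staff followed the row, report it as missing for that reason and keep it separate from loss to follow-up.

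The cost is one table row and a data-completeness check. No clinical procedure needs to be chosen here; the request is only that outcome measurement be stated consistently across arms.
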